#### PHD FELLOWSHIP FUNDAMENTAL RESEARCH - FWO

#### **Rationale And Positioning With Regard To The State-Of-The-Art**

Shoulder pain is the third most common musculoskeletal disorder, with lifetime prevalence ranging from 10% to 67%  and high reoccurrence rate of 41% after 1 year from the initial presentation . The socio-economic burden of shoulder pain is mainly due to sick leave, representing 84% of the total cost per patient in a Swedish cost-of-illness study. On the other hand, the mean healthcare cost is 326 euros per patient with physiotherapy accounting for 60%. Currently, non-operative management in form of physiotherapist-led exercises is the primary choice of treatment  $^{5}$  and subacromial shoulder pain (SSP) is the most commonly diagnosed shoulder complaint . However, it is not clear which are the best types of exercise, and in particular if pain should be elicited or avoided during exercise . In the current framework of the concept "hurt not equalling harm" , we propose that the therapeutic modality of "exercising into discomfort" has strong benefit in the treatment of SSP. Numerous studies have been conducted on SSP but none has investigated the specific role of exercising into discomfort on shoulder pain and functionality. Therefore, the main aim of the current proposal is to investigate the effectiveness of exercising into discomfort in order to achieve faster and superior benefits in pain and function. Patients and physiotherapists will be the first beneficiaries of this project: reconceptualising the role of pain in exercise therapy will improve the conservative treatment in SSP, leading to postpone or even avoid surgery and reducing the high recurrence rate and healthcare costs. If successful, this can be proposed in the future for the management of other chronic tendinopathies.

Previous studies have clearly shown that shoulder exercises are the preferred first choice of treatment for patients with SSP 5,10-13. National guidelines recommend active rehabilitation strategies for at least three months and limited use of glucocorticoid injection . Numerous systematic reviews have been conducted on different modalities of exercise therapy in terms on specific muscle-activation (scapularfocused approach ), type of contractions (eccentric exercises ) or training modalities (such as stabilization or proprioception ), but no strong recommendations on the superiority of one approach to another can be drawn. A review of systematic reviews suggested that loaded exercises and higher doses could provide superior benefits. Another recent systematic review advocated that exercising into discomfort in general musculoskeletal chronic pain could facilitate the reconceptualization of pain by addressing fear avoidance, self-efficacy and catastrophizing beliefs within a framework of "hurt not equalling harm". The rationale behind this approach lies on the analgesic effect of exercise as a form of endogenous pain modulation, which increases the pain threshold and reduces the pain intensity ratings through endogenous opioids and endocannabinoid mechanisms, occurring at peripheral, spinal and/or central sites . Moreover, exercising a de-conditioned tissue allows the central nervous system (CNS) to reprocess the perceived painful stimuli into a new positive perception so the painful movement can be reintroduced progressively .

The experience of discomfort during training is already well-documented in the rehabilitation of lower limb tendinopathies: significant improvements were reported in RCTs where the progression and load of exercises were individually prescribed using the pain monitoring system (through the Visual Analogue Scale, VAS or Numeric Pain Rating Scale NPRS) for both patellofemoral pain  and Achilles tendinopathies . Similarly, in shoulder rehabilitation research, promising results were found in an RCT comparing specific (loaded) exercises versus non-specific exercises in patients with subacromial impingement syndrome . The authors reported a reduced need for surgery at 1 and 5 years of follow-up , and a significantly greater improvement of pain and shoulder function in the specific exercise group, in whom the pain monitoring model was used to score the individual resistance for each patient. However, in all previous studies pain during exercises was never exceeding 5/10 on VAS scale, even in studies which claim to test a painful strategy versus a non-painful one . Hence, the role played by pain during exercise is not clear and since different exercises are equally clinically successful, it is more important to give individualized loaded exercises instead of one-size fits all programs, whatever the concept is (motor control, eccentric exercises, scapular exercises). Despite the potential of

resistance training, it remains uncertain what dose of resistance should be given and whether the patient will benefit from having some discomfort/pain during the training or not.  Therefore, the first objective of this project is to test the effectiveness of exercising into discomfort in a strength training program on pain and function.

The uncertainty in the best-evidence practice is also due to the multifactorial aetiology of SSP. The major hypothesis is that a reduction of the space between the acromion and the glenohumeral joint, the so-called subacromial space, causes an encroachment of the soft tissues during arm elevation, often referred to as "shoulder impingement" . The subacromial tissues mainly involved are the rotator cuff (RC) tendons,  encountering degeneration and inflammation . However, this anatomical "impingement" theory does not sufficiently explain the pathophysiology , which in fact displays a multifactorial aetiology. Both intrinsic and extrinsic mechanisms are involved in SSP; the former in terms of degeneration of the tendon itself, the latter in terms of compression of the RC tendons. Intrinsic factors are linked to tendon degeneration, due to the natural process of aging, altered biology, genetic predisposition and tendon mechanical properties . Extrinsic factors originate externally from the RC tendons and include anatomical variants of the acromion, alterations of humeral or scapular kinematics (named scapular dyskinesis), muscle imbalance, postural deviations and soft tissue tightness. In particular, scapular dyskinesis is a key component in the production of symptoms in SSP, in association with muscle imbalance or inadequate activation patterns (i.e. decreased activity of the serratus anterior and lower trapezius, and overactivation of the upper trapezius) . However, the presence of scapular dyskinesis is not always associated with changes in shoulder symptoms and function during and after the rehabilitation. Therefore, the second objective is to investigate whether improvements in shoulder pain, function and quality of life is positively related with reduced presence of scapular dyskinesis.

In this context, ultrasound (US) imaging has the potential to quantify the changes in the subacromial space and in the tendon structures during the rehabilitation process. US is able to characterize tissue using high-frequency sound waves, which is typically between 5 and 12 MHz in the musculoskeletal field . It has numerous advantages: it is non-invasive and non-radiating compared to radiography or computed tomography (CT) scan, cheaper and with higher image resolution than Magnetic Resonance Imaging (MRI), and available also as portable device . On the other hand, it is highly operatordependent and artifacts on the US image, such as anisotropy in tendon examination, can easily be encountered . Nevertheless, a standardized procedure and a thorough training can minimize these pitfalls . The subacromial space can be measured by US imaging as the articular distance between the acromion and the humeral head, called the acromiohumeral distance (AHD) . This measurement has shown to be reliable and sensitive . US can also detect tendon thickening, which is a sign of tendinopathy. Numerous studies have specifically analysed the supraspinatus tendon thickness (STT), as this is the RC tendon mostly involved in SSP . Although contrasting results have been found regarding differences in the STT between symptomatic and asymptomatic participants , it is possible that thicker tendons are more apparent in early stages of SSP and thinner in later stages . In contrast, a systematic review concluded that RC abnormalities, such as degeneration or thinning, occur equally in symptomatic and asymptomatic populations, suggesting that these changes are part of the normal aging process . Moreover, the interplay between STT and subacromial space was recently described as an occupation ratio, which represents the proportion of the subacromial space occupied by STT. This ratio was higher in patients with SSP, showing that STT occupied a greater percentage of the subacromial space. However, until present the mechanistic role of the subacromial space and its relationship with RC tendons thickness has not been studied in relation to the recovery process of SSP. This could however provide useful knowledge on the working mechanisms of SSP therapy. Therefore, the third objective is to examine the effects of exercising into discomfort on changes in subacromial space (quantified as acromiohumeral distance -AHD-) and tendon structures measured by US imaging in SSP patients. As such, unravelling the factors contributing to the SSP recovery process will help clinicians to better steer their therapy and adapt therapeutic parameters during physiotherapy.

The relationship between clinical symptoms and tendon structural changes/subacromial space is a matter of great debate. Contrasting results are present in the literature regarding the relationship between subacromial space (measured as AHD) and functional improvement, with some studies showing a strong correlation  and others suggesting the opposite . However, the relationships between AHD and functional improvements during and after treatment has not been largely explored and it warrants further investigations . Concerning the association between STT and clinical outcomes, increased STT has been linked to decreased muscle strength and palpable tenderness , making it a reproducible parameter of tendon state during the rehabilitation process. In daily general practice, combining clinical information with US findings could aid the prescription of tailored exercises for SSP patients, leading to improved patient outcomes. **Therefore, in the fourth objective this study will elucidate the relationship between US findings and clinical symptoms during and after 'exercising into discomfort'.** 

In summary, although physiotherapy offers promising results in the recovery of SSP, it is still not clear which type of exercise provides the best outcome and whether the patient should feel discomfort during the performance of an exercise, or pain should be avoided. This project aims to provide clinical evidence for the 'exercise into discomfort' approach, which can influence the entire concept of the management of SSP, contributing to the development of the best evidence-based practice in physiotherapy and reducing the relative healthcare costs of SSP. If this concept is proven to be successful, it confirms how the body's analgesic system is able to tackle its own pain similarly to other chronic pathologies such as patellofemoral pain or low back pain. This project will rely on both clinical outcomes (pain, function, scapular dyskinesis) and objective measures of subacromial space and RC tendon changes acquired with US. In this way, we will be able to track the evolution of subjective and objective changes happening during and after the rehabilitation process and how the presence of pain/discomfort during exercise influences them.

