# **Scientific Research Objectives**

The primary aim of this project is to provide proof-of-concept for the clinical effectiveness of the "exercising into discomfort" approach in patients with SSP. In the first three objectives, the focus will be on its effect on shoulder pain and functionality (patient-reported outcomes, objective 1), on scapular dyskinesis (objective 2), subacromial space, and the tendon structures (objective 3) during and after 3 months of exercise therapy in patients with SSP. In the fourth objective, the relationship between patient reported outcomes and the US measurements during the treatment course will be explored. Two groups will be compared in a randomized controlled trial (RCT): an intervention group "exercising into discomfort" (G1) and a control group "exercising without discomfort" (G2). The time points of assessment will be prior to the treatment at baseline (T0), at 6 weeks during treatment (T1), end of treatment at 12 weeks (T2), and follow up at 26 weeks (T3).

OBJECTIVE 1	To investigate the effectiveness of exercising into discomfort during a strength training program in the treatment of SSP on self-reported shoulder pain and function
Methods	Double Blind Randomized Controlled Trial comparing 2 groups (G1 versus G2), with SPADI (Shoulder Pain and Disability Index, a valid and reliable patient-reported outcome measure of pain and disability  ) as primary outcome. A "high pain monitoring model" will be used to monitor pain during and 1 hour after every exercise in G1 (see "intervention" in methodology).
Hypothesis	In G1 SPADI will be reduced more than in G2.
Novelty/ Relevance	If successful, the results of this study will lead to a reconceptualization of exercises in SSP, allowing pain (defined as discomfort sensation) to be an essential component and not a barrier in the physiotherapy treatment.

OBJECTIVE 2 ft	To investigate whether improvements in shoulder pain, function and quality of life is positively related with reduced presence of scapular dyskinesis
Methods	Scapular dyskinesis will be registered by visual observation at rest and during movements (abduction and flexion) and its effects on pain will be tested by scapular assistance test and scapular retraction test
Hypothesis	Scapular dyskinesis will decrease more in G1, in relation to the increase in strength and coordination of the scapulothoracic and scapulohumeral muscles.

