Novelty/ relevance	Although the scapular control will be integrated in the exercises in both groups from the first session, we expect a greater improvement in G1 thanks to both increased muscle strength and regained self-efficacy in movement performance. Therefore, it is relevant to register how scapular dyskinesis is evolving during treatment in order to understand when and in which subgroups of patients it is contributing to symptoms of SSP.

OBJECTIVE 3	To investigate the effects of exercising into discomfort on changes in subacromial space (quantified as acromiohumeral distance AHD) and tendon structures measured by US imaging in SSP patients							
MethodsAnalysis of the secondary outcomes (subacromial space and tendon structure changes measured by US imaging) of the RCT conducted in objective 1								
Hypothesis	In both groups there will be an increase in the subacromial space and decrease in STT. These changes will be more evident in G1							
Novelty/ Relevance	The lack of understanding of tendon structural changes in "exercising into discomfort" in patients with SSP contributes to the inadequate management of this pathology. Information on such parameters will provide insights into the mechanisms behind this modality of exercise therapy during and after the end of the treatment. Moreover, this study aims to clarify the role of the subacromial space as a valuable indicator of SSP recovery. To the best of our knowledge, this is the first time that tendon structures are monitored during the treatment other than before and after rehabilitation (assessment at T2).							

OBJECTIVE 4 උ	To examine whether improvement in shoulder pain, function and quality of life is associated with changes in the subacromial space and tendon structures as measured by US imaging
Methods	Analysis of possible association between parameters measured by US (subacromial space, RC tendon thickness) and clinical symptoms (self-reported shoulder pain, questionnaires on functionality and quality of life) at T0, T1, T2, T3 in the RCT
Hypothesis	There will be a significant correlation between US imaging parameters and clinical symptoms

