# WP3: Data analysis

Statistical analyses will be performed using JMP ®Pro 14.0.0 (SAS Institute Inc., Cary, NC, USA) . Level of significance is set at p= 0.05. Appropriate descriptive statistics will be performed.

**OBJECTIVE 1,2,3:** A mixed regression model for repeated measures will be used to assess both the evolution of SPADI (pain and function), strength, ROM and US parameters within persons from baseline (T0) over time (T1, T2, T3) and the differences in evolution between subjects. Potential confounders are: age, gender, BMI, previous corticosteroid injections, severity of initial symptoms. They will be measured during the history taking at the first assessment and added into the mixed regression model as co-variants. If for a certain variable the percentage of missingness will be more than 15%, multiple imputation for missed observation will be used. There are three assumptions for the mixed regression model: change over time, a sensible measure for time (multiple time points of measure), normality of residuals (it will be checked using a Shapiro-Wilk test). If these residuals are not normally distributed, an appropriate transformation will be performed first. Therefore, this model best fits the longitudinal design of the RCT. **OBJECTIVE 4**: correlation analysis between tendon structures and clinical symptoms using the correlation for pairs of continuous variables in JMP.

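### Objective 4 correlates ultrasound change with symptom change without adjusting for randomised group, although the plan expects the intervention arm (G1) to move both; the inflation is modest and cheap to remove

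*Combined protocol and SAP*

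**What the plan says.** The rationale introduces the fourth objective by saying that "this study will elucidate the relationship between US findings and clinical symptoms during and after 'exercising into discomfort".

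In WP3: Data analysis, Objectives 1 to 3 get a repeated-measures mixed model. The plan lists what may confound it: "Potential confounders are: age, gender, BMI, previous corticosteroid injections, severity of initial symptoms". These are to be "added into the mixed regression model as co-variants". Objective 4 gets a single sentence: "correlation analysis between tendon structures and clinical symptoms using the correlation for pairs of continuous variables in JMP". That sentence names no group term, no analysis within arms and no covariate. The 2022 renewal adds nothing on this point.

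The hypotheses under Scientific Research Objectives are:

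- Objective 1: "In G1 SPADI will be reduced more than in G2".
- Objective 3, on the increase in subacromial space and the decrease in supraspinatus thickness: "These changes will be more evident in G1".
- Objective 4: "There will be a significant correlation between US imaging parameters and clinical symptoms".

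The formal aim of Objective 4 relates clinical improvement to ultrasound change, using the four visits of the trial. It does not say whether the arms are pooled. Pooling is the natural reading, since no arm is named.

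**The concern.** By the plan's own hypotheses, randomised group is a cause of both variables that Objective 4 correlates. If Objectives 1 and 3 succeed, G1 patients lie further along both axes than G2 patients. A pooled scatter then tilts even if, inside each arm, a patient's ultrasound change says nothing about that patient's recovery. Success on Objectives 1 and 3 would therefore itself push Objective 4 towards its hypothesised result.

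What is at stake is interpretation. The plan wants to learn whether subacromial space is a useful indicator of recovery, to help clinicians tailor exercise, and to prepare prognostic studies. A correlation that partly reflects a shared treatment effect does not support those uses in the way that a within-arm association would.

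**Working it through.** **Figures in the plan.** No sample size, power or expected correlation is stated for Objective 4, so there is no figure to reproduce. The SPADI sample sizes (54, later 44) cannot be rerun, because no SD is given.

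**Inputs.**

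- n = 44, the revised target in the renewal (WP2: RCT).
- n = 37 after the plan's 15% drop-out (44 × 0.85 = 37.4).
- Significance level 0.05; two-sided is assumed.
- Two arms; 1:1 allocation is assumed.
- Direction of the group effects: the hypotheses of Objectives 1 and 3. Their size in SD units, d1 on SPADI change and d2 on ultrasound change, is assumed.
- One reference value for d1: under a simple two-sample formula, 44 patients at 85% power detect (1.96 + 1.036) × √(4/44) = 0.90 SD. The plan's own method is longitudinal, so this is only a guide. The Sample size section calls its original 8-point target moderate.

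**Correlation induced by group alone.** With zero correlation inside each arm and unit within-arm SD, the pooled covariance is d1·d2/4 and the pooled variances are 1 + d1²/4 and 1 + d2²/4. In absolute value,

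r = d1·d2 / √[(d1² + 4)(d2² + 4)].

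- 0.5 and 0.5: 0.25 / 4.25 = 0.06
- 0.9 and 0.5: 0.45 / √(4.81 × 4.25) = 0.10
- 0.9 and 0.9: 0.81 / 4.81 = 0.17

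**False-positive rate per test**, from simulated trials with no within-arm link:

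| Assumed effect, SPADI / ultrasound (SD) | Raw, n = 44 | Raw, n = 37 | Group partialled out, n = 44 |
|---|---|---|---|
| 0.5 / 0.5 | 6.9% | 6.3% | about 5% |
| 0.9 / 0.5 | 9.9% | 9.3% | about 5% |
| 0.9 / 0.9 | 19.6% | 17.0% | about 5% |

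**When group alone would be expected to give significance.** The critical r at n = 44 is 0.297. Setting d²/(d² + 4) = 0.297 gives d = √(4 × 0.297 / 0.703) = 1.30 SD on both variables. At n = 37 the critical r is 0.325 and d is about 1.4.

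**Baseline.** Allocation has had no effect at T0, so group cannot confound a T0 correlation. Age could, through the product of its correlations with the two variables, but the documents give neither. As a range of assumptions at n = 44: 0.2 with each gives an induced r of 0.04 and about 6% false positives; 0.3 gives 0.09 and about 9%; 0.5 gives 0.25 and about 38%.

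**The case against.** **The effect is small.** At 0.5 SD on both variables the error rate moves only from 5% to about 7%. The 20% figure needs 0.9 SD on ultrasound as well, which no document supports. The renewal also cuts the painful exercises from four to one of four, which makes a large group effect on tendon structure less likely. This stands, and it limits the size of the point. A reader might infer that group or age alone would deliver the hypothesised significant correlation. The 1.3 SD threshold shows that the documents do not support that.

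**The plan asks only about association.** If treatment moves both variables, the pooled association is real, and conditioning on group answers a different question. This stands in part: the raw correlation is a legitimate description and should stay. It is not enough for the mechanistic and prognostic uses that the plan has in mind.

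**The age argument is thin.** The rationale does say of cuff abnormalities that a review found them common to people with and without symptoms, "suggesting that these changes are part of the normal aging process". That gives no link from age to symptom severity. What remains is mainly that the plan itself lists age as a potential confounder.

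**There is no commitment to a G1-only estimate.** A reader might infer from the rationale that the relationship was to be estimated in G1 and has been left out. The formal objective carries no such restriction. A G1-only slope would rest on about 22 patients, where the critical r is about 0.42 and 80% power needs a true r of about 0.57.

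**Stacking the visits.** A reader might also suppose that the four visits will be treated as independent rows. The plan does not say so, and that would be a separate problem.

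**Conclusion.** The point holds in a limited form. The Objective 4 sentence omits randomised group although the plan's own hypotheses make group a common cause of both sets of post-baseline changes. As planned, the correlation cannot separate a within-arm link from a shared treatment effect.

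The size is a per-test error rate of about 7% to 10% in the more plausible of the assumed scenarios, and about 20% in one for which the documents offer no support on the ultrasound side. This rests on pooling of the arms, 1:1 allocation, two-sided testing and assumed standardised effects. T0 associations are untouched by group; for them, confounding by age is possible but unquantified.

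The introduction to the objectives describes Objective 4 as exploratory, and the primary SPADI analysis does not depend on it. The case for change is that a better analysis is available from data already planned, at almost no cost.

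**What to change.** Amend the Objective 4 sentence in WP3: Data analysis as follows.

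- For changes from T0 to T1, T2 and T3, make the main analysis a partial correlation or regression of symptom change on ultrasound change, adjusted for randomised group. Add age and gender, which the plan already names and collects, as further covariates.
- Run it with one row per patient at each time point. Report the estimate with a 95% CI beside the raw correlation.
- Adjust T0 associations for age and gender.
- Do not carry over the whole covariate list from Objectives 1 to 3, because initial severity is itself a clinical symptom at T0.
- A G1-only slope may be reported descriptively, noting that it rests on about 22 patients.

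The cost is one degree of freedom for group and up to three with age and gender, plus a change of wording. No new data are needed. The renewal puts unblinding at the end of the trial in November 2022, so on that timeline the change could be fixed before allocation is known.
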